9.2.1. Sensitivity Analyses

For the analyses of the key secondary variables, mean changes from baseline in T25FW, TUG and 2MWT, the MMRM model (Protocol Section 14.4.2) will be used based on available data

and there will be no imputation of missing values. These analyses effectively assume that the missing observations are missing at random (MAR). For each parameter, two sensitivity analyses will be conducted using a multiple imputation (MI) approach. The first sensitivity analysis will assume the data are MAR and will include additional covariates (Age, Duration of MS) in the imputation step that could be predictive of response and/or the probability of missingness. The second sensitivity analysis will assume the data are not missing at random (NMAR) and missing observations in the ADS-5102 treatment group will be imputed as if they had been obtained in the placebo treatment group.

9.3. Secondary Supportive Efficacy Analyses

The supportive secondary endpoints are the mean changes from Baseline between treatment groups at Weeks 8, 12, and 16 for the T25FW (s) and Weeks 8 and 12 for the T25FW (feet/second), TUG (s), and 2MWT (m). These are described in [Section 3.2.2.2](#).

Each active dose will be compared to placebo in terms of the mean change from baseline at each study visit in the T25FW (both feet/sec and sec), TUG test, and the 2MWT. These analyses will be done using the MMRM model described earlier.

9.4. Other Efficacy Analyses

9.4.1. Multiple Sclerosis Walking Scale -12

Descriptive statistics (n, mean, median, standard deviation, minimum, and maximum) will be provided for the MSWS-12 total score by study visit.

For this scale, each of the twelve items can be answered with five options with 1 meaning no limitation and 5 meaning extreme limitation. The total score is generated and transformed to a 0 to 100 scale by subtracting the minimum score possible (12) from the subject's score, dividing by the maximum score possible minus the minimum possible ($60 - 12 = 48$), and multiplying the result by 100. Walking improvement on the MSWS-12 is indicated by negative change scores.

9.4.2. Change in Walking Speed using T25FW

The percent change in average walking speed from Baseline to Week 16 using the T25FW will be calculated by treatment group and presented in a summary table. The difference in the percent change in average walking speed between placebo and active drug (137 mg ADS-5102 and 274 mg ADS-5102) will be analyzed. Point estimates, 95% confidence intervals, and p-values will be presented.

10. Safety Analyses

10.1. Adverse Events

Adverse events (AE) will be recorded starting from the date/time of first dose during the Single-Blind Placebo Run-In Period through the End of Study (EOS) Visit. The time periods of AE

recording will be divided into AEs with onset during the Single-Blind Placebo Run-In Period and AEs with onset during the Double-Blind Treatment Period.

A Treatment-Emergent Adverse Event (TEAE) is defined as an adverse event that begins or worsens in severity on or after the date of randomization.

Incidence of TEAEs during the Double-Blind Treatment Period (as well as number and percentage of subjects with TEAEs) will be tabulated according to Medical Dictionary for Regulatory Activities (MedDRA) by system organ class (SOC) and preferred term (PT) and will include the following categories:

- All TEAEs
- Most Commonly Reported TEAEs ($\geq 5\%$ in any treatment group) (by PT only)
- TEAEs by Relatedness to Study Drug
- TEAEs by Severity
- TEAEs Leading to Study Drug Discontinuation
- Serious TEAEs Leading to Study Drug Discontinuation by Relatedness to Study Drug
- Serious TEAEs by Relatedness to Study Drug
- Study Drug-Related Serious TEAEs
- TEAEs of Special Interest

MedDRA dictionary Version 21.0 will be used for reporting and will be described in the relevant table and listing footnotes.

Subjects with the same AE more than once will have that event counted only once within each System organ class (SOC) and Preferred term (PT). Subjects with the same AE more than once will have the maximum intensity of that event counted within each SOC and once within each PT for summaries of severity.

SOCs and PTs within SOC will be presented by descending frequency based on the ADS-5102 274 mg and ADS-5102 137 mg groups combined.

An overall summary AE table will include the numbers and percentages of subjects who had at least one of each of the following: TEAE, serious TEAE, study drug-related TEAE, TEAE leading to study drug discontinuation, serious TEAE leading to study drug discontinuation, study drug-related serious TEAE, AE of special interest, or on-study death.

TEAEs that have missing severity will be classified in table summaries as severe. Similarly, TEAEs that have missing relationship to study drug will be classified in table summaries as related.

All AEs will be listed by subject and period.

The three AE categories listed below are considered adverse events of special interest (AESI):

- Suicidality
- Hallucinations
- Events Potentially Related to Orthostatic Hypotension.

For each of the AESIs listed above, an additional data listing will be provided to include additional information collected in the clinical database for each type of AESI. Death Adverse events resulting in death will be provided in a separate data listing.

10.2. Clinical Laboratory Evaluations

The clinical laboratory assessments relating to safety to be performed include those for Hematology, and Serum Chemistry.

Laboratory assessments for hematology and serum chemistry will be performed by a central laboratory. All summaries will be based on the International System (SI) units provided by the central lab. No unit conversions will be made.

All clinical laboratory measures will be classified using the following alert flags:

- LP - Low Panic
- LT - Low Telephone
- LN - Low Normal
- N – Normal
- HP - High Panic
- HT - High Telephone
- HN - High Normal
- AB - Abnormal

10.2.1. Hematology

The number and percentage of subjects with any potentially clinically significant changes from baseline will be tabulated and summarized by treatment group.

Table 2: Potential Clinical Significance (PCS) for Hematology Parameters

Laboratory Parameter	Flag	Criteria*	
		Observed Value	Change from Baseline
Hemoglobin	High (CH)	$> 1.3 \times \text{ULN}$	> 30% Increase from Baseline
	Low (CL)	$< 0.8 \times \text{LLN}$	> 20% Decrease from Baseline
Hematocrit	High (CH)	$> 1.3 \times \text{ULN}$	> 30% Increase from Baseline
	Low (CL)	$< 0.8 \times \text{LLN}$	> 20% Decrease from Baseline
Erythrocyte count (RBC)	High (CH)	$> 1.3 \times \text{ULN}$	> 30% Increase from Baseline
	Low (CL)	$< 0.8 \times \text{LLN}$	> 20% Decrease from Baseline
Mean corpuscular Volume (MCV)	High (CH)	$> 1.15 \times \text{ULN}$	> 15% Increase from Baseline

Laboratory Parameter	Flag	Criteria*	
		Observed Value	Change from Baseline
	Low (CL)	$< 0.85 \times \text{LLN}$	$> 15\%$ Decrease from Baseline
Mean corpuscular hemoglobin (MCH)	High (CH)	$> 1.15 \times \text{ULN}$	$> 15\%$ Increase from Baseline
	Low (CL)	$< 0.85 \times \text{LLN}$	$> 15\%$ Decrease from Baseline
Mean corpuscular hemoglobin concentration (MCHC)	High (CH)	$> 1.15 \times \text{ULN}$	$> 15\%$ Increase from Baseline
	Low (CL)	$< 0.85 \times \text{LLN}$	$> 15\%$ Decrease from Baseline
Leukocyte count (WBC)	High (CH)	$> 1.6 \times \text{ULN}$	$> 100\%$ Increase from Baseline
	Low (CL)	$< 0.65 \times \text{LLN}$	$> 60\%$ Decrease from Baseline
Neutrophils	High (CH)	$> 1.6 \times \text{ULN}$	$> 100\%$ Increase from Baseline
	Low (CL)	$< 0.65 \times \text{LLN}$	$> 75\%$ Decrease from Baseline
Lymphocytes	High (CH)	$> 1.5 \times \text{ULN}$	$> 100\%$ Increase from Baseline
	Low (CL)	$< 0.25 \times \text{LLN}$	$> 75\%$ Decrease from Baseline
Eosinophils	High (CH)	$> 4.0 \times \text{ULN}$	$> 300\%$ Increase from Baseline
	Low (CL)	N/A	N/A
Monocytes	High (CH)	$> 4.0 \times \text{ULN}$	$> 300\%$ Increase from Baseline
	Low (CL)	N/A	N/A
Basophils	High (CH)	$> 4.0 \times \text{ULN}$	$> 300\%$ Increase from Baseline
	Low (CL)	N/A	N/A
Platelets	High (CH)	$> 1.5 \times \text{ULN}$	$> 100\%$ Increase from Baseline
	Low (CL)	$< 0.65 \times \text{LLN}$	$> 50\%$ Decrease from Baseline

Notes: PCS = potentially clinically significant

CH = high PCS based on criterion value and increase from predose.

CL = low PCS based on criterion value and decrease from predose.

*A postdose value is considered as a PCS value if it meets both criteria for observed value and change from predose.

Hematology data will also be provided via data listings.

10.2.2. Serum Chemistry

The number and percentage of subjects with any potentially clinically significant changes from baseline will be tabulated and summarized by treatment group.

Table 3: Potential Clinical Significance (PCS) for Serum Chemistry Parameters

Laboratory Parameter	Flag	Criteria*	
		Observed Value	Change from Baseline
Bicarbonate	High (CH)	$> 1.3 \times \text{ULN}$	$> 40\%$ Increase from Baseline

Laboratory Parameter	Flag	Criteria*	
		Observed Value	Change from Baseline
	Low (CL)	$< 0.7 \times \text{LLN}$	$> 40\%$ Decrease from Baseline
Sodium	High (CH)	$> 1.1 \times \text{ULN}$	$> 10\%$ Increase from Baseline
	Low (CL)	$< 0.85 \times \text{LLN}$	$> 10\%$ Decrease from Baseline
Potassium	High (CH)	$> 1.2 \times \text{ULN}$	$> 20\%$ Increase from Baseline
	Low (CL)	$< 0.8 \times \text{LLN}$	$> 20\%$ Decrease from Baseline
Phosphorus	High (CH)	$> 3.0 \times \text{ULN}$	$> 200\%$ Increase from Baseline
	Low (CL)	$< 0.5 \times \text{LLN}$	$> 50\%$ Decrease from Baseline
Chloride	High (CH)	$> 1.2 \times \text{ULN}$	$> 20\%$ Increase from Baseline
	Low (CL)	$< 0.8 \times \text{LLN}$	$> 20\%$ Decrease from Baseline
Calcium	High (CH)	$> 1.3 \times \text{ULN}$	$> 30\%$ Increase from Baseline
	Low (CL)	$< 0.7 \times \text{LLN}$	$> 30\%$ Decrease from Baseline
Alkaline phosphatase (ALP)	High (CH)	$> 2.0 \times \text{ULN}$	$> 100\%$ Increase from Baseline
	Low (CL)	$< 0.5 \times \text{LLN}$	$> 80\%$ Decrease from Baseline
Alanine Aminotransferase (ALT)	High (CH)	$> 3.0 \times \text{ULN}$	$> 200\%$ Increase from Baseline
	Low (CL)	N/A	N/A
Aspartate Aminotransferase (AST)	High (CH)	$> 3.0 \times \text{ULN}$	$> 200\%$ Increase from Baseline
	Low (CL)	N/A	N/A
Gamma-glutamyl transferase	High (CH)	$> 3.0 \times \text{ULN}$	$> 200\%$ Increase from Baseline
	Low (CL)	N/A	N/A
Lactate Dehydrogenase (LDH)	High (CH)	$> 4.0 \times \text{ULN}$	$> 300\%$ Increase from Baseline
	Low (CL)	$< 0.4 \times \text{LLN}$	$> 60\%$ Decrease from Baseline
Bilirubin, Total	High (CH)	$> 2.5 \times \text{ULN}$	$> 150\%$ Increase from Baseline
	Low (CL)	N/A	N/A
Glucose, non-fasting	High (CH)	$> 3.0 \times \text{ULN}$	$> 200\%$ Increase from Baseline
	Low (CL)	$< 0.6 \times \text{LLN}$	$> 40\%$ Decrease from Baseline
Protein, Total	High (CH)	$> 1.5 \times \text{ULN}$	$> 50\%$ Increase from Baseline
	Low (CL)	$< 0.5 \times \text{LLN}$	$> 50\%$ Decrease from Baseline
Albumin	High (CH)	$> 1.5 \times \text{ULN}$	$> 50\%$ Increase from Baseline
	Low (CL)	$< 0.5 \times \text{LLN}$	$> 50\%$ Decrease from Baseline
Serum creatinine	High (CH)	$> 2.0 \times \text{ULN}$	$> 100\%$ Increase from Baseline
	Low (CL)	$< 0.3 \times \text{LLN}$	$> 100\%$ Decrease from Baseline
Blood Urea Nitrogen (BUN)	High (CH)	$> 3.0 \times \text{ULN}$	$> 200\%$ Increase from Baseline
	Low (CL)	$< 0.2 \times \text{LLN}$	$> 100\%$ Decrease from Baseline

Notes: PCS = potentially clinically significant

CH = high PCS based on criterion value and increase from predose.

Laboratory Parameter	Flag	Criteria*	
		Observed Value	Change from Baseline

CL = low PCS based on criterion value and decrease from predose.

*A postdose value is considered as a PCS value if it meets both criteria for observed value and change from predose.

Serum chemistry data will also be provided via data listings.

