18. Presence of orthostatic hypotension at screening: a decrease in systolic blood pressure (at least 20 mm Hg) or diastolic blood pressure (at least 10 mm Hg) within 3 minutes of the subject standing up, compared to pressures obtained while sitting
19. Any laboratory test results outside of the central laboratory's normal range at screening that are assessed by the investigator to be clinically significant. Documentation by the investigator of clinical significance or insignificance must accompany out of range laboratory test results at screening
20. Aspartate aminotransferase (AST) and/or alanine aminotransferase (ALT) screening laboratory results > 2 times the upper limit of normal
21. Estimated glomerular filtration rate (eGFR) < 60 mL/min/1.73 m² (per Modification of Diet in Renal Disease [MDRD] calculation)
22. Inability to swallow oral capsules, or a history of gastrointestinal malabsorption that would preclude the use of oral medication
23. If female, is pregnant or lactating
24. If a sexually active female, is not surgically sterile or at least 2 years post-menopausal, or does not agree to utilize a highly effective hormonal method of contraception (an IUD, or vasectomized male partner is also acceptable), in combination with a barrier method, from screening through at least 4 weeks after the completion of study treatment. If a sexually active male, does not agree to utilize condoms from screening through at least 4 weeks after the completion of study treatment.
25. Received live attenuated influenza vaccine within 2 weeks prior to randomization or planning to receive live attenuated influenza vaccine during the duration of the study (amantadine may interfere with the efficacy of live attenuated vaccine)

26. Current treatment with medications that may affect urinary pH: carbonic anhydrase inhibitors, sodium bicarbonate, urinary acidification agents, quinine, quinidine, triamterene, or trimethoprim
27. Treatment with an investigational drug or device within 30 days prior to screening
28. Treatment with an investigational biologic within 6 months or 5 half-lives, whichever is longer, prior to screening
29. Current participation in another clinical trial
30. Prior or current participation in an Adamas clinical trial
31. Planned elective surgery, with the exception of minor dermatological procedures, during study participation

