11.2. Clinical Laboratory Tests

The clinical laboratory and other tests relating to safety to be performed during the study are described in the following table. The estimated total blood volume collected throughout the study (for clinical laboratory tests) is expected to be approximately 30 mL for safety serum chemistry and hematology laboratory evaluations.

Table 6: Clinical Laboratory and Other Assessments

Assessment	Study Visit	Description
Hematology	Screening Week 16 (or ET)	Blood samples (5 mL) will be collected. Hematology parameters include: hemoglobin, hematocrit, mean corpuscular volume (MCV), mean corpuscular hemoglobin concentration (MCHC), red blood cell (RBC) count, white blood cell (WBC) count, WBC differential count, and platelet count. Hematology will be conducted by a central laboratory.
Serum Chemistry	Screening Week 16 (or ET)	Blood samples (10 mL) will be collected (fasting is not required). Routine serum chemistry parameters include alkaline phosphatase, albumin, blood urea nitrogen, calcium, carbon dioxide, chloride, creatinine, γ -glutamyl transferase, glucose, inorganic phosphorus, potassium, alanine aminotransferase, lactate dehydrogenase, aspartate aminotransferase, sodium, total bilirubin, and total protein.
Urinalysis	Screening Week 16 (or ET)	Urinalysis will be performed using sponsor-supplied dipsticks, including leukocytes, specific gravity, pH, protein, ketones, glucose, nitrite, blood, urobilinogen, and bilirubin. If nitrite, blood, or protein tests are positive, a microscopic examination will be performed.
Serum pregnancy test (if applicable)	Screening Week 16 (or ET) Safety Follow-Up	Serum pregnancy test will be performed for all female subjects of childbearing potential.
Urine pregnancy test (if applicable)	Week 0, Week 2 Baseline/Week 4	Urine pregnancy test will be performed for all female subjects of childbearing potential.

Estimated glomerular filtration rate (eGFR) will be calculated by the central laboratory using MDRD.

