4.1. Dose Adjustment/Modifications

Dose Adjustment for Renal Impairment

Subjects whose estimated glomerular filtration rate (eGFR) falls below 60 mL/min/1.73 m², confirmed by repeat testing, should discontinue study drug. These subjects should be encouraged to complete study visits per the protocol.

Dose Adjustment for Adverse Events

Study drug may only be withheld for the evaluation or treatment of an AE. If, in the judgement of the investigator, study drug should be withheld for the evaluation or treatment of an AE, the investigator may have the subject do so for up to 3 consecutive days, and is then to have the subject resume dosing at the same dose level. If, in the judgement of the investigator, study drug needs to be withheld for more than 3 consecutive days, the investigator must contact one of the study's Medical Monitors to determine whether drug may be withheld for a longer period or the subject should be permanently discontinued from study drug. Study drug may not be down-

titrated. This procedure applies to the withholding of study drug throughout the study with the exception of the titration phase of the Double-Blind Treatment Period.

In the special case of study drug being withheld for the evaluation or treatment of an AE occurring during the titration phase of the Double-Blind Treatment Period (i.e., Week 4 to Week 6), the investigator may have the subject do so for up to 3 consecutive days, and is then to have the subject resume dosing at the same dose level. The subject is to finish the remaining capsules in the blister card, i.e., including the 2-dose overage. The subject must return to the clinic to receive his or her next blister pack without missing any additional doses. If, in the judgement of the investigator, study drug needs to be withheld for more than 3 consecutive days, the subject is to be permanently discontinued from study drug.

5. General Statistical Considerations

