5.8. Unscheduled Visits

Data collected at unscheduled visits will be displayed in data listings and used to calculate maximum/minimum values, as applicable, but will not be displayed in summaries presented by study visit.

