5.11.5. Laboratory Data Imputations

If a lab value is reported using a non-numeric qualifier (e.g., less than [<] a certain value, or greater than [>] a certain value), the given numeric value will be used in the summary statistics, ignoring the non-numeric qualifier. For instance, a value reported as “<200” would be listed as such, but summarized as “200.”

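### SAP Table 3: the low PCS flags for serum creatinine and BUN require a fall of more than 100%, so neither can ever be met

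*Combined protocol and SAP*

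**What the plan says.** SAP 10.2.2 commits to a by-arm safety tabulation: "The number and percentage of subjects with any potentially clinically significant changes from baseline will be tabulated and summarized by treatment group". Table 3 supplies the criteria, one for the observed value and one for the change from baseline.

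- Serum creatinine, low: observed value below 0.3 × LLN, with "> 100\%$ Decrease from Baseline".
- BUN, low: observed value below 0.2 × LLN, with the same change criterion.

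The footnote joins the two columns: "A postdose value is considered as a PCS value if it meets both criteria for observed value and change from predose". The note defining the low flag says the same.

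Where the plan does not want a low flag, it enters N/A in both columns. In Table 3 this is done for ALT, AST, gamma-glutamyl transferase and total bilirubin. In Table 2 it is done for eosinophils, monocytes and basophils. Creatinine and BUN carry numeric limits instead, so they are presented as working flags.

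Under SAP 5.4, laboratory baseline is the latest available value up to and including the day of randomization.

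**The concern.** A concentration cannot be negative, so a fall of more than all of it is impossible. Because the footnote requires both criteria, the impossible one disables the whole flag, however low the observed value is.

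What is at stake is how one safety table is read. Nobody will be flagged low for creatinine or BUN in any arm, whatever the data show. Someone who reads that table without working through the criteria could take it as evidence that no marked falls occurred.

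**Working it through.** **Inputs.** From SAP Table 3: the limits 0.3 × LLN (creatinine) and 0.2 × LLN (BUN), the required fall of more than 100%, and the footnote joining the criteria by AND. The plan states a threshold here, not a calculated result, so there is no figure to reproduce.

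**Step 1: the largest possible fall.** With baseline B > 0 and post-dose value V ≥ 0,

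fall (%) = 100 × (B − V) / B.

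This is largest at V = 0, where it equals 100 × B / B = 100%. A fall above 100% needs V < 0. A grid check with B from 0.01 to 100 and V from 0 to 100 found no fall above 100%. The inequality in the table is strict, so even V = 0 fails.

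**Step 2: a worked case.** Take a baseline at the LLN and a post-dose value of 0.1 × LLN. The value is below both observed-value limits. The fall is 100 × (1 − 0.1) / 1 = 90%, which is not above 100%, so neither flag is set. For a baseline at the LLN, just reaching the observed-value limit is already a fall of 1 − 0.3 = 70% for creatinine and 1 − 0.2 = 80% for BUN.

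**Step 3: the other low rows.** Multiplier of LLN, then required fall:

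- Table 3 (11 rows): bicarbonate 0.7, 40%; sodium 0.85, 10%; potassium 0.8, 20%; phosphorus 0.5, 50%; chloride 0.8, 20%; calcium 0.7, 30%; ALP 0.5, 80%; LDH 0.4, 60%; glucose 0.6, 40%; total protein 0.5, 50%; albumin 0.5, 50%. Range 10% to 80%.
- Table 2 (10 rows): hemoglobin, hematocrit and RBC 0.8, 20%; MCV, MCH and MCHC 0.85, 15%; WBC 0.65, 60%; neutrophils 0.65, 75%; lymphocytes 0.25, 75%; platelets 0.65, 50%. Range 15% to 75%.

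All 11 + 10 = 21 rows are attainable. Table 3 has 13 numeric low rows, and 2 of the 13 are not. In 8 of the 11 attainable Table 3 rows the required fall equals 1 minus the multiplier (all except bicarbonate, sodium and ALP). This suggests that the two 100% cells are a slip, but it does not show what was intended.

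**Step 4: alternative readings.**

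- Criteria joined by OR: the observed-value limit could then fire alone, but the footnote rules this out.
- Fall taken relative to the post-dose value: more than 100% would mean V < B/2 and could occur, but the column is defined as change from baseline.
- At least 100% in place of more than 100%: the flag would fire only at a value of exactly zero.

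The documents give no other definition of percentage decrease and no exception for these two analytes.

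**Result.** The count for each of the two low flags is 0 in every arm, regardless of the data.

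**The case against.** The arithmetic is not in dispute. The case on the other side is that little follows from it, and most of that case stands.

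- A reader might infer that the table will display two misleading zeros. The documents do not establish this. SAP 5.13 shows every category only when it is specified on the CRF or is an ordered interval. Other categorical data appear only where the frequency is not zero, and percentages are suppressed at zero counts. Derived PCS flags may well fall in the second group, and no table shell is available to settle it. An omitted row can still be taken to mean that nothing was found, so the point survives in either layout.
- A reader might infer that very low values would go unseen. That is not supported either. SAP 10.2 gives every laboratory measure an alert flag, including low categories. Protocol 14.5 flags values outside the reference range, SAP 10.2.2 provides listings, and protocol 13.2.1 requires clinically significant out-of-range findings to be recorded as AEs. Only the by-arm PCS count is lost.
- A reader might infer that PCS reporting for these two analytes has failed altogether. It has not. The high flags (creatinine above 2.0 × ULN with a rise of more than 100%; BUN above 3.0 × ULN with a rise of more than 200%) can both be met.
- The observed-value limits are extreme, and nothing in the documents suggests that any subject would reach them. This is fair, and it limits the importance of the point without making the criterion workable.

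One supporting argument is not needed. SAP 5.11.5 says of results reported below a limit that "the given numeric value will be used in the summary statistics, ignoring the non-numeric qualifier". That rule keeps such values positive, but it concerns summary statistics and not PCS flags. The conclusion holds without it, because a value of zero already fails.

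**Conclusion.** The point holds in a limited form. Two of the 13 numeric low rows in SAP Table 3 cannot be met as written, so their by-arm counts are fixed at zero before any data are seen. The absence of flagged subjects in those rows carries no information about safety. This rests only on concentrations not being negative and on the SAP's own footnote and column definition.

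The size is small. The effect is confined to two rows of one safety tabulation, and no efficacy result changes. The documents do not show how many subjects, if any, an attainable criterion would flag, so no missed safety signal is claimed.

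**What to change.** In SAP Table 3, do one of the following for the serum creatinine and BUN low rows, before unblinding:

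- replace the two change-from-baseline cells with an attainable percentage chosen by the sponsor; or
- set both low rows to N/A in both columns, as the table already does for ALT, AST, gamma-glutamyl transferase and total bilirubin.

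The first option keeps a working low flag and needs the sponsor to settle the percentage. The second gives up the low flag but makes that plain to the reader. Either is an edit to two table rows plus the matching program change. No new data are needed.

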14.5. Safety and Tolerability

Adverse events will be recorded starting from the date/time of first dose during the Single-Blind Placebo Run-In Period through the EOS Visit. The time periods of AE recording will be divided into AEs with onset during the Single-Blind Placebo Run-In Period and AEs during the Double-Blind Treatment Period (i.e., TEAEs). All AEs will be listed by subject and period.

For AEs during double-blind treatment, standard incidence rates will be summarized by treatment group, system organ class (SOC) and preferred term (PT) within SOC in the safety analysis set. This includes all subjects who received at least one dose of double-blind study drug according to the treatment arm actually received.

Incidence of TEAEs will be summarized for:

- All TEAEs
- Investigator-determined treatment-related TEAEs
- TEAEs leading to drug discontinuation
- TEAEs by severity
- Serious TEAEs (SAEs)
- Investigator- determined treatment-related SAEs
- Discontinuation due to SAEs

Clinical laboratory test parameters will be listed for individual subjects and values outside of the reference ranges will be flagged. Descriptive statistics for the mean and mean changes from baseline at each study week will be generated by treatment group. The incidence of potentially clinically significant changes in laboratory parameters will be tabulated by treatment group. Vital signs measurements at each timepoint will be listed by subject. The incidence of potentially clinically significant changes at each study visit will be summarized.

Descriptive statistics for the mean and mean changes in the C-SSRS will be generated by treatment group and visit. Results will also be depicted graphically.

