5.4. Baseline

For endpoints based on the T25FW, Baseline will be defined as the average of up to two separate visit averages (each based on up to two measurements taken five minutes apart) collected at Weeks 2 and 4 (prior to randomization). If one of the two T25FW Baselines values is missing, then Baseline will be defined as the last non-missing measurement prior to or on the date of randomization.

For endpoints based on the TUG, 2MWT, and MSWS-12, Baseline will be defined as the average of up to two separate measurements collected at Weeks 2 and 4 (prior to randomization). If one of the two TUG, 2MWT and/or MSWS-12 Baselines values is missing, Baseline will be defined as the last non-missing measurement prior to or on the date of randomization.

For C-SSRS analyses, the questionnaire three-year history data obtained during the Screening visit will be considered Baseline.

For all other endpoints, Baseline is defined as the last non-missing measurement prior to or on the date of randomization.

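### SAP 10.2 omits, without declaring it, the by-arm laboratory mean-change summary planned in protocol 14.5; the PCS counts left have baseline-dependent thresholds, and two low flags can never fire

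*Combined protocol and SAP*

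**What the plan says.** Protocol Section 14.5 says of laboratory parameters: "Descriptive statistics for the mean and mean changes from baseline at each study week will be generated by treatment group". It also plans the incidence of potentially clinically significant changes by treatment group. The SAP introduction says the SAP is based on protocol Section 14.

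SAP Section 10.2 assigns alert flags to laboratory values. For hematology (10.2.1) and serum chemistry (10.2.2) it then specifies one summary: "The number and percentage of subjects with any potentially clinically significant changes from baseline will be tabulated and summarized by treatment group". The data are otherwise listed. No laboratory mean or mean change appears there, and SAP Section 11, which lists departures from the protocol, does not mention the omission. SAP Section 5.11.5 nevertheless explains how a qualified laboratory value enters summary statistics.

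Tables 2 and 3 give each flag an observed-value limit and a change-from-baseline limit. The footnote to each table joins them: "A postdose value is considered as a PCS value if it meets both criteria for observed value and change from predose".

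On entry, protocol exclusion 20 names AST and/or ALT "screening laboratory results > 2 times the upper limit of normal", so values up to 2 x ULN are admissible. Exclusion 19 also removes "Any laboratory test results outside of the central laboratory's normal range at screening that are assessed by the investigator to be clinically significant".

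**The concern.** If the mean-change table is not produced, a small systematic shift in a laboratory parameter on active drug has no planned by-arm display. The PCS counts that remain address individual extremes, but under a rule whose effective limit moves with the subject's own baseline. A reader of the table would see, for example, 3 x ULN for ALT or 0.65 x LLN for neutrophils, and could take a zero count to mean that no subject passed that limit. For some baselines that inference would be wrong. For the low creatinine and BUN flags a zero count is guaranteed and carries no information.

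**Working it through.** The documents state no effective threshold, so there is no figure of theirs to reproduce. The inputs are the paired limits in SAP Tables 2 and 3, the both-criteria footnote, and the protocol's entry limits. The laboratory baseline comes from SAP 5.4: "For all other endpoints, Baseline is defined as the last non-missing measurement prior to or on the date of randomization". Scheduled hematology and chemistry are drawn only at Screening and at Week 16 or early termination (protocol Table 6 and Appendix A), so baseline is normally the screening value.

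Let b be baseline in multiples of ULN (high flags) or LLN (low flags). When both criteria are required:

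- high flag: value > max(observed limit, (1 + increase) x b)
- low flag: value < min(observed limit, (1 - decrease) x b)
- the two criteria coincide at b = observed limit / (1 + increase) for high flags, or observed limit / (1 - decrease) for low flags.

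**ALT and AST, high** (> 3.0 x ULN and > 200% increase): the threshold is max(3, 3b) x ULN.

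- b at or below 1.0: 3.0
- b = 1.25: 3.75
- b = 1.5: 4.5
- b = 1.75: 5.25
- b = 2.0: 6.0

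For a baseline at or below ULN the change criterion adds nothing. Above ULN it can only remove flags. A rise from 2.0 to 5.9 x ULN is 5.9/2.0 - 1 = 195% and is not counted.

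**Low counts with a 0.65 x LLN limit:**

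- Neutrophils (> 75% fall): min(0.65, 0.25b). This is 0.25 at b = 1 and 0.375 at b = 1.5. The printed limit governs above b = 0.65/0.25 = 2.6.
- WBC (> 60% fall): min(0.65, 0.40b). This is 0.40 at b = 1 and 0.48 at b = 1.2. The printed limit governs above b = 0.65/0.40 = 1.625.
- Platelets (> 50% fall): min(0.65, 0.50b). This is 0.50 at b = 1 and 0.55 at b = 1.1. The printed limit governs above b = 0.65/0.50 = 1.3.

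A neutrophil fall from 1.5 to 0.4 x LLN is 1 - 0.4/1.5 = 73% and is not counted.

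**Low flags that work as printed:** lymphocytes, 0.25/(1 - 0.75) = 1.0; hemoglobin, hematocrit and RBC, 0.8/(1 - 0.20) = 1.0. For any baseline at or above LLN the printed limit is the operating limit.

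**Creatinine and BUN, low** (< 0.3 and < 0.2 x LLN, each with > 100% decrease): the second criterion requires a value below (1 - 1.00) x baseline = 0. No concentration can be negative, so neither flag can occur.

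**The case against.** The strongest reply is that the tables openly state a two-part rule. The protocol asks for clinically significant changes, and combining level with change is a legitimate way to define them. How strict to be is a trade of sensitivity against specificity, applied equally in all arms. That stands: nothing printed is being overridden, and the two-criterion row can stay.

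A reader might infer that the trial cannot detect ALT or AST below 6 x ULN. The documents do not support that. Six times ULN applies only at a baseline of exactly 2 x ULN; normal baselines keep the 3 x ULN limit, and exclusion 19 may remove some subjects in between. Every value stays in the listings and SAP 10.2 assigns alert flags, including panic levels. Under protocol 13.2.1 a finding judged clinically significant must be recorded as an adverse event, and SAP 10.1 tabulates treatment-emergent events by arm. These routes are only a partial substitute: SAP 10.2 defines no by-arm tabulation of alert flags, and protocol 13.2.1 says out-of-range results are not adverse events in themselves and that clinical significance usually goes with a sign or symptom.

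A reader might also infer that the mean-change analysis was deliberately dropped. SAP 5.11.5 still presupposes laboratory summary statistics, SAP 5.11 speaks generally of tabulating available safety data, and the protocol synopsis does not carry the mean-change sentence. An unreconciled inconsistency is the fair description. Nor would mean changes back up the individual flags: means show systematic shift, not outliers, so the two gaps need separate remedies.

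**Conclusion.** The point holds in limited form. SAP 10.2 does not specify the laboratory mean-change summary of protocol 14.5, and Section 11 does not declare the difference. The remaining by-arm laboratory tabulation in SAP 10.2 has an effective ALT/AST limit that slides from 3 to 6 x ULN over admissible baselines of 1 to 2 x ULN, and effective low limits for neutrophils, WBC and platelets that are stricter than 0.65 x LLN below the baselines shown. Two low flags are impossible.

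The thresholds follow from the SAP's own limits, taking the screening value as baseline. The number of subjects affected cannot be estimated: the documents give neither the share with ALT or AST between 1 and 2 x ULN nor the distribution of baseline counts. So they do not support a claim that any given number of events would be missed, or that one arm would be favored. The efficacy analyses are unaffected. The change is worth making because it is cheap and alters what the by-arm laboratory comparison can show.

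**What to change.** 1. Restore in SAP 10.2 a by-arm table of the mean and the mean change from baseline at Week 16 or early termination, for all hematology and chemistry parameters. If the sponsor intends to omit it, declare that in Section 11 and reconcile Section 5.11.5.
2. Keep the two-criterion PCS row. Beside it, for every parameter in Tables 2 and 3, add a by-arm count of subjects whose post-baseline value meets the observed-value criterion alone. Covering all parameters avoids a selective choice, and showing both rows lets the reader separate level from change.
3. Replace the > 100% decrease criteria for creatinine and BUN with attainable ones, or mark those low flags as not applicable, as Table 3 already does for ALT and AST.

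The cost is SAP wording and a few standard tables, with no new data or visits. The downside is that the added row will count some values in subjects whose baseline was already abnormal or borderline, in all arms.
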